8.3.2 Assessment of causality

AEs will be evaluated for whether they meet the criteria for an adverse reaction (AR). An AR is a response to IMP which is noxious and unintended, and which occurs at any dose. The term "reaction" means that a causal relationship between IMP and an adverse event is at least a reasonable possibility. This

means that there are facts (evidence) or arguments to suggest a causal relationship.

- The Investigator will use clinical judgment to determine the relationship.
- Alternative causes, such as underlying disease(s), concomitant therapy, and other risk factors, as well as the temporal relationship of the event to IMP administration must be assessed.
- The Investigator will also consult the Investigator's Brochure (IB)/SmPC in his/her assessment.
- For each AE/SAE, the Investigator must document in the medical notes that he/she has reviewed the AE/SAE and has provided an assessment of causality.
- There may be situations in which an SAE has occurred, and the Investigator has minimal information to include in the initial report to Upstream Bio. However, it is important that the Investigator attempts to make an assessment of causality before the initial transmission of the SAE data to the Sponsor or designee.
- This is due to the fact that the causality assessment is one of the criteria used when determining regulatory reporting requirements.
- The Investigator may change his/her opinion of causality in light of follow-up information and send an SAE follow-up report with the updated causality assessment.

The causality assessment of an AE to the IMP will be rated as follows by the Investigator:

Definitely: A reaction that follows a reasonable temporal sequence from administration of study drug; that follows a known or expected response pattern to the study drug; it disappears or decreases on cessation or reduction in study drug dose; and/or it reappears or worsens when the study drug is administered.

Probably: A reaction that follows a reasonable temporal sequence from administration of study drug; that follows a known or expected response pattern to the study drug; and/or that could not be reasonably explained by other factors such as underlying disease, complications, concomitant drugs, or concurrent treatments.

Possibly: A reaction that follows a reasonable temporal sequence from administration of study drug; that follows a known or expected response pattern to the study drug, but that could reasonably have been produced by a number of other factors including underlying disease, complications, concomitant drugs, or concurrent treatments.

Not Related: A reaction for which sufficient data exist to indicate that the aetiology is unrelated to the study drug.

The Investigator should also comment on the source document whether an AE is not related to the study treatment but is related to study participation (e.g., study procedures).

The relationship to the study medication will be classified according to the categories described in Table 16.

8.3.3 Practical application of severity grading and causality assessment in relation to AR rules

Step 1: Confirm diagnosis of the AE/AR (exact term will be decided using the MedDRA), once the root cause of the clinical manifestations has been determined (rather than diagnosing individual signs, symptoms, assessments, and measurements).

Step 2: Distinguish between serious and non-serious AE/ARs using the standard definitions of what constitutes a 'serious' AE/AR (see Section 8.2).

Step 3: Assess whether there is a reasonable possibility of a relationship with the IMP.

Step 4: If there is a reasonable possibility that it is related to the IMP, apply the correct AR rules

- **'serious AR':** The classification as 'serious' (see Sections 8.2 and 8.3) overrides the application of the categorical (mild/moderate/severe) grading system. The rules for serious AR must be applied. Categorical grading (moderate or severe) should also be independently recorded to add additional information.
- **'non-serious AR':**
 - some individual clinical manifestations, signs, symptoms, assessments, or measurements (such as QT prolongation, anaemia, thrombocytopenia, liver enzyme abnormalities) have pre-defined special AR rules, which should be applied if they occur
 - for all other non-serious ARs use the global clinical assessment and categorical grading method outlined above to assign the severity grade (Table 16). Consider:
 - the clinical significance (including presence or absence of clinical symptoms)
 - participant populations' specific references ranges and degree of deviations thereof
 - the degree of deviations from baseline
 - timing, duration, and reversibility
 - the nature and intensity of treatment required and the responses to the treatment; in addition, the potential to worsen or to become defined as serious
 - apply the general AR rules according to the assigned categorical severity grade.

8.3.4 Expectedness (Reference Safety Information)

No SARs are considered expected by the Sponsor for the purpose of expedited reporting of SUSARs.

8.4 Adverse Events of Special Interest

An Adverse Event of Special Interest (AESI) is an adverse event of scientific or medical concern specific to the Sponsor or the particular product or program, for which ongoing monitoring and rapid communication by the Investigator to the Sponsor may be appropriate. It may require further investigation in order to characterize and understand them. It could be serious or non-serious and could include events that might be potential precursors or prodromes for more serious medical conditions in susceptible individuals. If an AESI is serious, reporting procedures for SAE/SUSAR will be used. For non-serious AESI, reporting procedures will be described in the SOM.

For this study, AESIs based on the class of drugs include:

- Allergic reactions.
- Immune complex disease.
- Severe infections which are defined as:
 - Life-threatening or,
 - Requiring hospitalization or,
 - Requiring treatment with antiviral medications, IV antibiotics or medications for helminth parasitic infection or,
 - Requiring a permanent discontinuation of study drug.
- Injection site reactions graded moderate in severity or higher.

8.5 Recording of adverse events and follow-up

All (serious and non-serious) adverse events detected by the investigator or spontaneously notified by the participant at each visit/examination must be reported on the appropriate pages of the CRF. The following information should be reported for each adverse event, whether or not it can be attributed to study drug:

- Description of adverse event
- Date of onset/date of resolution
- Characteristics of the event (seriousness, intensity)
- Actions taken (treatment required, or dose adjustments must be reported in the CRF)
- Outcome
- Relationship with study drug (causality assessment) and/or study participation

A clinical laboratory abnormality will be reported as an AE if deemed to be clinically significant by the Investigator. Examples that suggest clinical significance include:

- Accompanied by clinical symptoms
- Leading to a change in treatment with IMP (e.g., dose modification, interruption, permanent discontinuation)

- Requiring a change in concomitant therapy (e.g., addition of, interruption of, discontinuation of, any other change in a concomitant medication, therapy, or treatment)
- The abnormality suggests a disease and/or organ toxicity
- The abnormality is of a degree that requires active management (e.g., discontinuation of IMP, more frequent follow-up assessments, further diagnostic investigation)

All AEs must be followed until the event is either resolved or a satisfactory explanation is found, a new baseline is met, the participant withdraws consent for participation in the study, participant is lost to follow-up, or the investigator considers it medically justifiable to terminate the follow-up. The reason(s) will be recorded in the CRF when the AE follow-up is terminated.

Whenever possible, a diagnosis should be recorded as the AE term rather than a series of symptoms/terms relating to a diagnosis. However, if the diagnosis is unknown, record sign(s) and/or symptom(s). If a diagnosis subsequently becomes available, the diagnosis should be recorded, replacing the original entry(s) where appropriate.

8.6 Reporting of Serious Adverse Events

Detailed reporting procedures will be outlined in the pharmacovigilance plan.

If an SAE occurs, the Investigators will take appropriate action immediately and will strive to identify the cause(s) of the events.

All SAEs/SUSARs will be notified by the Investigator to the Sponsor within 24 hours of awareness by email to:

[REDACTED]
using the 'Serious Adverse Event Form'. Emails sent to the above address will be automatically forwarded on receipt to the Upstream Bio Medical Monitor plus other individuals detailed in the Safety Management Plan.

The SAE follow-up observation period, for the concerned participants, will be jointly decided by the Investigator, Sponsor and/or SRC.

The initial report will be followed up by a full written report within 3 working days or 5 calendar days, whichever is sooner, unless no further information is available. In that case, the follow-up report will be provided as soon as new information becomes available. Further follow-up reports will be provided as and when new information becomes available. Photocopies of relevant CRF pages, such as demography, medical history, concomitant medications, as well as test results, consultant report(s), a summary of the outcome of the reaction and the Investigator's opinion of IMP relationship to the SAE/SUSAR will accompany the SAE form if and when available.

The Sponsor will also perform an evaluation of all SAEs prior to their finalization and/or reporting to any third party (e.g., REC, agency).

SUSARs will be notified to the Competent Authority and to the relevant REC(s) by Upstream Bio or its representatives within 7 days for fatal and life-threatening SUSARs or 15 days all other SUSARs.

Annual safety reporting to the national Competent Authority and the REC will be in compliance with ICH guideline E2F 'Note for guidance on Development Safety Update Reports (DSUR)'.

8.7 Potential drug-induced liver injury

Participants with DILI defined as AST or ALT $\geq 3 \times$ ULN; total bilirubin $\geq 2 \times$ ULN; absence of biliary obstruction/cholestasis (alkaline phosphatase $< 2 \times$ ULN) and no other explanation for the findings (e.g., viral hepatitis, chronic or acute liver disease, administration of concomitant hepatotoxic drug) must be reported as an SAE.

8.8 Pregnancy

Pregnancy is not regarded as an AE, unless there is a suspicion that the IMP may have interfered with the effectiveness of a contraceptive medication. However, complications of pregnancy and abnormal outcomes of pregnancy are AEs, and many may meet criteria for an SAE. Complications of pregnancy and abnormal outcomes of pregnancy, such as ectopic pregnancy, spontaneous abortion, intrauterine foetal demise, neonatal death, or congenital anomaly, would meet the criteria of an SAE and therefore should be reported as an SAE. Elective abortions without complications should not be handled as an AE.

If a participant becomes or is found to be pregnant while being treated or exposed to study drug, the Investigator must submit the 'Pregnancy Report Form' to the Sponsor via the same method as SAE reporting.

The participant should be followed until the outcome of the pregnancy is known (spontaneous miscarriage, elective termination, normal birth or congenital abnormality). When the outcome of the pregnancy becomes known, the Investigator must submit the 'Pregnancy Outcome Form' to the Sponsor via the same method as SAE reporting. If additional follow-up of the participant is required, the Investigator will be requested to provide the information.

Participants who are WOCBP will be instructed to report to the Sponsor any pregnancy that occurs between the final D85 Visit and D120 post-dose. Participants who are WOCBP will agree at the time of Informed Consent to perform a pregnancy test on Day 120 post-dose and inform the investigator of the result. In order to support this requirement, participants who are WOCBP will be provided with a home pregnancy testing kit at Day 85 (or at their Final Visit in cases of early withdrawal). More details regarding the Day 120 pregnancy testing process will be included in the SOM.

8.8.1 Pregnancy in female partners of male participants

If a male participant's female partner becomes or is found to be pregnant while the participant was being treated or exposed to study drug, the Investigator must submit the 'Pregnancy Report Form' to the Sponsor via the same method as SAE reporting.

Male participants may continue in the study if an accidental pregnancy of their female partner occurs despite adequate contraception.

If the male participant's partner signs informed consent, they should be followed until the outcome of the pregnancy is known (spontaneous miscarriage, elective termination, normal birth or congenital abnormality), even if the male participant

withdraws from the study. When the outcome of the pregnancy becomes known, the Investigator must submit the 'Pregnancy Outcome Form' to transScrip via the same method as SAE reporting. If additional follow-up of the female partner is required, the Investigator will be requested to provide the information.

Male participants will be instructed to report to the Investigator any pregnancy in a WOCBP partner that occurs between the final D85 Visit and D120 post-dose.

9. QUALITY ASSURANCE AND QUALITY CONTROL

9.1 Quality assurance and quality control

Regulatory agencies may carry out a Regulatory Inspection of this study. Such audits/inspections can occur at any time during or after completion of the study. If an audit or inspection occurs, the PI and RPL agree to allow the auditor/inspector direct access to all relevant documents and to allocate their time and the time of their staff to the auditor/inspector to discuss any findings or relevant issues.

Quality Control (QC) procedures at the RPL will be implemented to ensure data recorded into the CRFs are accurate. QC checks will be carried out on an ongoing basis and according to the relevant SOPs. Records of QC checks will be documented and available for review.

Study documents routinely undergo QC to ensure their accuracy before being used and/or sent to the Sponsor. The RPL staff member providing the QC checks the documents and notes any findings/comments on the QC record form. QC checks will be carried out on an ongoing basis throughout the study and according to the relevant SOPs. Records of QC checks will be documented and available for review.

9.2 Monitoring

All aspects of the study will be carefully monitored by the Sponsor, or designee, for compliance with applicable government regulations with respect to Good Clinical Practice (GCP) and current Standard Operating Procedures.

The monitoring of this study will be performed by the Sponsor's monitor(s) or a designee in accordance with the principles of GCP as laid out in the International Council for Harmonisation of Technical Requirements for Pharmaceuticals for Human Use (ICH) Good Clinical Practice Guideline E6(R2) (2016).

The clinical monitor, as a representative of the Sponsor, has an obligation to follow the study closely. In doing so, the monitor will visit the Investigator and site periodically and will maintain frequent telephone and email contact. The monitor will maintain current personal knowledge of the study through observation, review of study records and source documentation, and discussion of the conduct of the study with the Investigator and staff. Further details will be described in the SOM.

10. STATISTICAL ANALYSIS

10.1 Statistical analysis plan

A Statistical Analysis Plan (SAP) containing detailed statistical methodology will be written and signed off before the database hard lock. The plan may be updated to reflect adaptive features of the study as appropriate.

10.2 Statistical hypotheses

No formal statistical hypotheses will be tested in this safety study.

10.3 Sample size determination

The primary objective of the study is to characterize and compare the PK of single doses of UPB-101 in Japanese and NJNEA adults. A sample size of 8 Japanese participants enrolled in each of treatment groups 1, 2, and 3 to be administered [redacted], [redacted], and [redacted] mg of UPB-101, respectively, and 8 NJNEA participants assigned [redacted] mg of UPB-101 to treatment group 4, is considered adequate to accomplish the primary objectives of the study. The sample size is not based on formal statistical hypothesis testing. A single treatment group of NJNEA participants is included to provide a comparison to the wider dataset. Data from this study may also be compared to data from the completed SAD study conducted in healthy, NJNEA adults and the currently ongoing MAD study in adult asthmatics.

10.4 Analysis sets

The analysis of data will be based on different analysis sets according to the purpose of analysis. Participant eligibility for each analysis set will be finalized before the database hard lock. A participant who withdraws prior to the last planned observation in a study period will be included in the analyses up to the time of discontinuation.

10.4.1 Safety set

The safety set will consist of all randomized participants who received at least one injection of the IMP. The safety set will be used for the safety analyses.

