3.2 Schedule of Assessments

Table 4: Schedule of Assessments

Period	Screening (D-21 to D-2)	Admission	Treatment												Follow up								
			D-1	D2	D3	D4	D5	D6	D7	D8	D9	D10	D11	D12	D13	D14	D15	D22	D29	D43	D57	D71	D85 / Final Visit
Procedure																							
Informed consent ^a	X																						
Demographic data	X																						
Medical/Surgical history and prior medications	X	X ^b																					
Urine drugs of abuse screen (including urine cotinine)	X	X																					
Smoking history (pack/year) and current	X																						
Breath alcohol test	X	X																					
Serology (HIV 1 & 2, Hep B & C)	X																						
Pregnancy testing (females) ^c	X	X																					
FSH (post-menopausal females) ^c	X																						
Quantiferon [®] -TB Gold test	X																						
Inclusion/Exclusion criteria	X	X ^b																					
Study Residency																							
Check-in		X																					
Check-out																							
Non-residential visit	X																						

Period	Screening (D-21 to D-2)		Treatment												Follow up									
	D-21	Admission	D-1	D2	D3	D4	D5	D6	D7	D8	D9	D10	D11	D12	D13	D14	D15	D22	D29	D43	D57	D71	D85 / Final Visit	
Randomization for treatment groups 1 to 3		X																						
Study drug administration ^d		X																						
Meals ^e		X	X	X	X	X	X	X	X	X	X	X	X	X	X	X	X							
Safety and tolerability:																								
AE recording/concomitant medication ^f																								
24h Holter ECG ^g	X																							
Telemetry ^h		X	X	X	X	X	X	X	X	X	X	X	X	X	X	X	X	X	X	X	X	X	X	
Vital signs ⁱ	X	X	X	X	X	X	X	X	X	X	X	X	X	X	X	X	X	X	X	X	X	X	X	
12-lead ECG ^j	X	X	X	X	X	X	X	X	X	X	X	X	X	X	X	X	X	X	X	X	X	X	X	
Body weight/height/BMI ^k	X	X ^k																						
Physical examination ^l	X	X	X	X	X	X	X	X	X	X	X	X	X	X	X	X	X	X	X	X	X	X	X	
Haematology/Biochemistry /Coagulation ^m	X	X	X														X							
Urinalysis	X	X																X						
COVID-19 testing ⁿ	X	X	X	X	X	X	X	X	X	X	X	X	X	X	X	X	X	X	X	X	X	X	X	
Assess injection site reactions ^o		X	X																					

Period	Screening (D-21 to D-2)	Admission	Treatment												Follow up							
Procedure	D-1	D2	D3	D4	D5	D6	D7	D8	D9	D10	D11	D12	D13	D14	D15	D22	D29	D43	D57	D71	D85 / Final Visit	
PK/PD/Immunogenicity assessments																						
PK blood sampling ^p		X	X	X	X	X	X	X	X	X	X	X	X	X	X	X	X	X	X	X	X	X
PD blood sampling ^q		X	X	X	X	X	X	X	X	X	X	X	X	X	X	X	X	X	X	X	X	X

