Serum ADA and Nabs (immunogenicity)				X ^r														X				X

- a) Procedures will not occur until informed consent is completed. Consent outside of the defined Screening window (D-21 to D-2) is allowed.
- b) Update only.
- c) Serum pregnancy testing is to be performed at Screening, Day -1 and Day 85 for WOCBP. At other visits, a urine pregnancy test is performed. All post-menopausal females will require an FSH serum test at Screening to confirm post-menopausal status.
- d) Study drug will be administered as a single dose on Day 1 via SC injection, according to the randomization schedule.
- e) On Day 1, breakfast will not be served. Lunch will be served after completion of H4 procedures. Dinner and snack will be served after completion of H8 procedures and at H12, respectively. Standard meals will be served at standard unit times from Day 2 to Day 14. On Day 15 (dismissal day), breakfast will be optional.
- f) AEs and concomitant medications will be collected at each visit from the time of consent until the end of study visit, and daily during study residency.
- g) A Holter ECG assessment must be performed at Screening to exclude pre-existing ECG abnormalities.
- h) Continuous 12-lead telemetry will be recorded from at least 1-hour pre-dose to 24 hours post-dose
- i) Vital signs (respiratory rate, tympanic temperature, blood pressure and heart rate) will be measured after at least 5 minutes rest in supine position, according to the timepoints in Table 5.
- j) 12-lead ECGs (triplicate) will be measured after at least 10 minutes rest in supine position, according to the detailed timepoints in Table 5.
- k) Height will be measured at Screening only.
- l) A Full Physical examination will be carried out at Screening and Day 85. Symptom-directed physical examinations will be performed at all other time-points.
- m) Pre-dose on Day 1. Additional unscheduled safety blood samples may be added at the investigator's discretion.
- n) COVID-19 testing will be carried out as per the site's latest COVID-19 Infection Control Guidelines and pre-entry algorithms.
- o) Injection site evaluations will be performed at pre-dose, 30 mins, 1-hour, 4-hour, 12-hour and 24-hour post-dose. Additional examinations may be performed as 'unscheduled' assessments, as required, until resolution of symptoms. Injection site photos will be taken at the same timepoints to monitor any changes.

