6.2 Treatment allocation

6.2.1 Participant randomization

All participants of Japanese ethnicity will be assigned to a treatment regimen according to a randomization schedule generated by a statistician using PROC Plan

(treatment groups 1-3). Randomization does not occur for participants in treatment group 4 as all NJNEA participants are assigned to the same treatment (█ mg UPB-101). Details regarding the unique Screening and participant number will be included in the SOM.

Eligible participants will be randomly assigned on Day 1 at the point of dosing. 8 participants will be randomized per treatment group. Thus, a total of approximately 32 male and female participants will be enrolled in the study with approximately 24 Japanese participants in treatment groups 1-3 and 8 NJNEA participants in treatment group 4.

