### Safety set

The Safety set will consist of all randomized participants who received at least one injection of the UPB-101. The safety set will be used for the safety analyses.

The Safety set will be used for the presentation of demographic summaries.

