## 3.4 Randomisation and Blinding

All participants of Japanese ethnicity will be assigned to a treatment regimen according to a randomization schedule generated by a statistician using PROC Plan (treatment groups 1-3). Randomization does not occur for participants in treatment group 4 as all NJNEA participants are assigned to the same treatment ([REDACTED] mg UPB-101). Details regarding the unique Screening and participant number will be included in the study operations manual (SOM).

Eligible participants will be randomly assigned on Day 1 at the point of dosing. 8 participants will be randomized per treatment group. Thus, a total of approximately 32 male and female participants will be enrolled in the study with

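### The Safety set, and every set nested in it, is limited to dosed randomized participants although group 4 (NJNEA) is not randomized: a minor wording error in an operative definition

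*Protocol*

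**What the plan says.** Protocol 10.4.1 defines the Safety set thus: "The safety set will consist of all randomized participants who received at least one injection of the IMP". SAP 3.2 has the same rule with the product named: "The Safety set will consist of all randomized participants who received at least one injection of the UPB-101". Both require two things, randomization and exposure.

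The PK and Immunogenicity sets (Protocol 10.4.2 and 10.4.4, SAP 3.2) are drawn from members of the Safety set. So is the PD set, which only the protocol defines (10.4.3).

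On assignment, Protocol 6.2.1 says: "Randomization does not occur for participants in treatment group 4 as all NJNEA participants are assigned to the same treatment". SAP 3.4 says the same. Table 4 in Protocol 3.2 labels the scheduled procedure "Randomization for treatment groups 1 to 3". Protocol 5.1 separates the two routes: Japanese participants are randomized and NJNEA participants are allocated.

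The same assignment sections also use the word more broadly. Protocol 6.2.1 continues: "8 participants will be randomized per treatment group. Thus, a total of approximately 32 male and female participants will be enrolled in the study". SAP 3.4 likewise has "8 participants will be randomized per treatment group".

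**The concern.** An analysis-set definition is a rule that a programmer applies to data. Here the rule has a condition that one whole group cannot meet under the plan's own description of assignment. That group is the sole comparator. The primary objective is to compare PK between Japanese and NJNEA adults, and the primary endpoint is assessed in the PK set. The secondary objectives make the same comparison for safety in the Safety set and for immunogenicity in the Immunogenicity set. Applied exactly as written, the definitions would leave no NJNEA data for any of these.

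The SAP carries the wording over unchanged, and its section on deviations from the protocol (4.15) does not address it.

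**Working it through.** **Inputs.** Four groups of 8 planned participants: groups 1 to 3 Japanese, group 4 NJNEA (Protocol 5.1 and 6.2.1, SAP Table 1). Groups 1 to 3 are randomized and group 4 is not (Protocol 6.2.1, SAP 3.4). Assumption: all planned participants are enrolled and dosed, with no replacements.

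**Reproducing the plan's total.** 4 × 8 = 32, made up of 3 × 8 = 24 Japanese and 8 NJNEA. This matches the stated enrolment.

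**Set membership under each reading**

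| Reading of the Safety set | Japanese | NJNEA | Total |
|---|---|---|---|
| Literal: randomized and dosed | 24 | 0 | 24 of 32 (24/32 = 75%) |
| Evident intent: all dosed | 24 | 8 | 32 of 32 (100%) |

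The literal reading drops 8/32 = 25% of planned participants, and all of them are in the comparator group. Since each nested set requires Safety set membership, NJNEA membership of the PK, Immunogenicity and PD sets is also 0.

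**Which reading is intended.** Protocol 10.5 and SAP 4.4 and 4.10.1 call for summaries by population group, Japanese versus NJNEA, on the Safety set. Those tables cannot be produced under the literal reading. The sentence that gives 8 randomized per group leads directly to a total of about 32, and 4 × 8 = 32 only if group 4 is counted. The word therefore has two senses in one section: groups 1 to 3 only, and everyone assigned.

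**What stays open once intent is accepted.** The disposition summary (protocol synopsis, SAP 4.3) reports the number and percentage randomized and treated. The planned randomized count is 24 under the strict sense and 32 under the loose one. Including group 4 in the Safety set does not settle which figure to print.

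No power or type I error figure is involved. Protocol 10.2 and 10.3 state that there is no formal test and that the sample size is not based on one.

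**The case against.** The strongest reply is that the documents resolve the ambiguity themselves. The study as a whole is called randomized, the assignment section counts all four groups as randomized, and NJNEA summaries are mandated. Set membership is finalized before hard lock (Protocol 10.4, SAP 3.2), then tabulated and listed by subject (SAP 4.3), so the loss of an entire group would be seen. This stands as an argument about likelihood and keeps the point minor. It does not make the definition correct: a reader should not need other sections to learn that a stated condition does not apply.

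Three stronger inferences are tempting, and the documents do not support them.

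- A reader might infer that eligibility violations in group 4 would go unlisted, because SAP 4.5 refers to randomised subjects. SAP 4.1 says that all collected data are presented in by-subject listings, which largely covers this.
- A reader might infer that dosed NJNEA participants would be screening failures kept out of the database, because Protocol 11.1 describes screening failures as consented but not randomized. Nobody would apply that reading to a dosed participant. The sentence is better taken as more evidence of loose usage than as a separate harm.
- A reader might treat 24 and 32 as upper limits. They are planned counts: withdrawn participants may be replaced and their evaluable data are kept (Protocol Table 6 and 5.2), so the numbers dosed can be higher.

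**Conclusion.** The definition is wrong as written in both documents, and the error passes to every nested set. Severity is minor. The literal consequence would be large, with 0 of 8 planned NJNEA participants in any analysis set, but it is very unlikely to occur, and under the evident intent no estimate changes. A reader might conclude that the primary comparison is actually at risk of losing its comparator; the population-group summaries and the four-group count of 32 speak plainly against that.

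The conclusion rests on the stated assignment rule for group 4 and on the planned group sizes. It does not depend on any redacted figure.

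**What to change.** In Protocol 10.4.1 and SAP 3.2, delete the word randomized, so that the Safety set is every participant given at least one injection of UPB-101. The nested definitions then need no change. Because the plan says "Eligible participants will be randomly assigned on Day 1 at the point of dosing", every Japanese participant dosed as planned is already randomized, so under the plan the deletion adds group 4 and nobody else.

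Optionally, have SAP 4.3 state that the disposition count is of participants randomized (groups 1 to 3) or allocated (group 4). This removes the choice between 24 and 32.

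Similar rewording in Protocol 6.2.1, Protocol 11.1, SAP 3.4, SAP 4.1, SAP 4.5 and Table 4 footnote d ("Study drug will be administered as a single dose on Day 1 via SC injection, according to the randomization schedule") would be for consistency only and is not needed to correct the sets.

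The cost is one word in each of two sentences, plus one optional clause. The exposure criterion, the data and the planned analyses are unchanged. SAP 4.15 refers to study completion in the past tense; if a protocol edit is no longer practical, the SAP can carry the correction or the clinical study report can note it.
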